##### 4.4.1 Major Permitted Therapies for NMO

##### **Permitted Medication/Therapy During the Double-Blind Period**

###### 1. Baseline treatment

One of the drugs listed below is required as monotherapy for baseline treatment at baseline. A dose must not exceed the dose defined below and a stable dose must be maintained. Dose decrease is permitted only for safety reasons. Dose increase or change of baseline treatment is not permitted.

- Azathioprine\*: 3 mg/kg/day
- Mycophenolate mofetil\*: 3000 mg/day
- Oral corticosteroids: 15 mg/day (prednisolone equivalent)

\* Combination with oral corticosteroids (15 mg/day [prednisolone equivalent]) is permitted in patients aged 12 to 17 years at the time of informed consent.

2. Rescue therapy for clinical relapse (leads to end of the double-blind period); pulse IV corticosteroids, intravenous immunoglobulin (IVIG), and/or apheresis (including plasma exchange and plasmapheresis).

Rescue therapy should proceed at the discretion of the treating Investigator after the examining assessor has completed EDSS/FSS assessment at extra visit at relapsing (except in case of emergency when urgent treatment is required before the patient can undergo this assessment).

3. Pain medications (including but not limited to pregabalin, gabapentin, carbamazepine, clonazepam, duloxetine, tramadol/acetaminophen).

Starting of pain medications is permitted, however the dose should be stable during the double-blind period. In case pain control is insufficient, dose increase or change of pain medication is permitted. Dose decrease and temporary treatment suspension are permitted for only safety reasons.

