### **Permitted Medication/Therapy During the Extension Period (Including After Relapse in the Double-Blind Period)**

1. Baseline treatment (for patients with no relapse in the double-blind period or extension period).

One of the drugs listed below is permitted as monotherapy for baseline treatment. The dose must not exceed the dose defined below. Change or termination of baseline treatment is permitted.

- Azathioprine\*: 3 mg/kg/day
- Mycophenolate mofetil\*: 3000 mg/day
- Oral corticosteroids: 15 mg/day (prednisolone equivalent)

\* Combination with oral corticosteroids (15 mg/day [prednisolone equivalent]) is permitted in patients aged 12 to 17 years at the time of informed consent.

2. Baseline treatment (for patients who have experienced relapse in the double-blind period or extension period).

One of the following maintenance treatments is permitted. The dose must not exceed the dose defined below. Change of baseline treatment is permitted.

- Azathioprine (3 mg/kg/day) ± oral corticosteroids (1 mg/kg/day; prednisolone equivalent).

Oral corticosteroid may be tapered off according to the standard local tapering regimen at the site.

- Mycophenolate mofetil (3000 mg/day) ± oral corticosteroids (1 mg/kg/day; prednisolone equivalent).  
Oral corticosteroid may be tapered off according to the standard local tapering regimen at the site.
  - Oral corticosteroids: 1 mg/kg/day (prednisolone equivalent).  
Oral corticosteroids may be tapered to 15 mg/day or less according to the standard local tapering regimen at the site.
3. Rescue therapy for clinical relapse; pulse IV corticosteroids, IVIG, and/or apheresis (including plasma exchange and plasmapheresis).  
Rescue therapy should proceed at the discretion of the treating Investigator after the examining assessor has completed EDSS/FSS assessment at extra visit at relapsing (except in case of emergency when urgent treatment is required before the patient can undergo this assessment). Satralizumab treatment can be continued as scheduled, concurrently with rescue therapy, unless the Investigator considers it necessary to withdraw the patient.
4. Pain medication (including but not limited to pregabalin, gabapentin, carbamazepine, clonazepam, duloxetine, tramadol/acetaminophen).
5. *During the OLE period: Treatment with corticosteroids (e.g., oral, nasal) for AEs (i.e., indications other than baseline therapy or rescue therapy) is permitted; the treatment duration should be kept as short as possible.*

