**Figure 2 Assessment of a Relapse**

The sequence of procedures of the extra visit at relapsing should be as follows:

- a. The assessment at the extra visit at relapsing, which is listed in [Appendix 1](#), is performed, where the EDSS/FSS is assessed by examining assessor.
  - i. If the symptom is of a clinical relapse as judged by Investigator, study drug should not be administered until the patient enters extension period.
- b. The symptom is confirmed whether it meets the criteria for a protocol-defined relapse.
- c. The Relapse Assessment Form will be completed and sent to the CEC (Please see [Section 4.5.3.3](#)).
- d. Rescue therapy should proceed at the discretion of the treating Investigator (the sequence may be different in case of an emergency).

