#### **5.1.1.1 Serious Infection**

In a Phase 1 multiple dose study of satralizumab in patients with RA (SA-105JP), one case of serious infection, bronchopneumonia (1 of 33 patients), was reported. Serious infection is an identified risk of tocilizumab. In the all-exposure population of tocilizumab, the most common serious infections included pneumonia, urinary tract infection, cellulitis, herpes zoster, gastroenteritis, diverticulitis, sepsis and bacterial arthritis.

Treatment with satralizumab suppresses acute phase reactions (fever, increase in CRP, etc.) induced by IL-6 and accordingly suppresses signs and symptoms associated with infection, which may delay the detection of infections. As a result, it may potentially make the infection more *severe*.

Patients with an active infection (excluding fungal infections of nail beds or caries dentium) within 4 weeks prior to baseline will be excluded from this study.

Patients with evidence of active TB (excluding patients receiving chemoprophylaxis for latent TB infection) will be excluded from this study.

Patients with chronic active hepatitis B or C will be excluded from this study.

Patients who received any live or live attenuated vaccine within 6 weeks prior to baseline will be excluded from this study.

- Satralizumab should not be initiated or administered in patients with active infections.
- Patients should be closely monitored for the development of signs and symptoms of infection, as signs and symptoms of acute inflammation may be lessened due to suppression of the acute phase reactants.

- Patients must be instructed to contact their physician immediately when any symptoms suggesting infection appear, in order to *ensure* rapid evaluation and appropriate treatment.
- If a patient develops a serious infection, administration of satralizumab is to be interrupted until the infection is resolved. The *treating physician* should *conduct a benefit-risk assessment* before resuming treatment with satralizumab.
- Live or live attenuated vaccines should not to be given within 6 weeks prior to baseline and during the course of the study as clinical safety has not been established.

For patients with NMO participating in this protocol, therapies used to treat NMO (corticosteroids, azathioprine, mycophenolate mofetil) have been shown to be associated with infections, particularly serious infections.

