5.2 General Presentation Considerations

Unless otherwise specified, Week 0 (Day 1) visit, which in most cases should correspond to the date of first dose, will be the baseline in the double-blind period, in which the baseline measurements will be collected at Day 1 prior to the first injection.

The date of first SA237 dose will be the baseline in the All-Subjects-Treated (All SA237) population analyses, in which the baseline measurements will be collected on the day of the first dose, prior to the study drug injection.

The definition of each duration for analysis is as follows:

- Double blind period for efficacy analysis
 - Double-blind period starts on the day of the randomization. The double-blind period ends on the earliest day of 1) clinical cutoff date (CCOD), 2) the day before the first

treatment in the extension period, 3) the end of the study, or 4) last contact for patients lost to follow up.

- Double blind period for safety analysis
 - Double blind period starts on the day of first dose of study drug. The double-blind period ends on the same day as efficacy analysis..
- SA237 exposure duration for safety analysis (for All SA237 analysis)
 - SA237 exposure duration starts on the day of first dose of SA237. SA237 exposure duration ends on the earliest day of 1) CCOD, 2) the end of the study, or 3) last contact for patients lost to follow up.

The definition of summaries by visit is as follows:

- Summaries by visit for double blind period
 - Baseline is defined as the latest data before the date of first administration for all data. Summarized visits except for baseline are defined as follows. Irregular visits such as unscheduled visit between week X, dose outside the visit window (DOW), extra visit at relapsing, and the end of the study are out of scope. Week X visits are directly used for categories of time. In other words, time window is not applied. If there are the same visits data, one representative assessment nearest to the scheduled visit day will be summarized.
- Summaries by visit for All SA237 analysis

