5.10.2 Primary Efficacy Variable

The primary efficacy analyses will be based on the ITT population. Supportive evaluations will be performed using the PPS population.

The primary efficacy endpoint is TFR based on protocol-defined relapses confirmed by the CEC with EDSS/FSS assessment performed by the examining assessor within 7 days after relapse symptoms were reported to site by the subject. TFR is defined as the time from the date of the randomization until the first occurrence of relapse throughout the study. Time point of relapse onset is defined as time at which the subject experiences any new or worsening neurological NMO representing clinical relapse(s) which is later confirmed by the CEC as protocol-defined.

Censor is defined as the earliest day of 1) the end of double blind period for efficacy analysis, 2) switching or increasing the baseline treatment (for details on the identification of the switch and increase in baseline therapy see appendix 7.4), or 3) receiving rescue therapy for clinical relapse.

The primary analysis of the study is to test the equality of the TFR distribution based on protocol-defined relapse in the SA237 + baseline treatment (SA237) and Placebo + baseline treatment (placebo) arms:

$$H_0: TFR_{SA237} = TFR_{\text{placebo}} \text{ versus } H_1: TFR_{SA237} \neq TFR_{\text{placebo}}$$

A stratified two-sided log-rank test using strata of baseline ARR (one vs. more than one) and geographical region (Asia and EU/Other) will be used.

The Kaplan-Meier method will be used to estimate the TFR based on protocol-defined relapses distribution for each treatment group. The Kaplan-Meier curve will provide a visual description of the differences across treatment groups. In addition, estimates of the treatment effect will be expressed as hazard ratio and 95% CIs using a stratified (baseline ARR and geographical region) Cox proportional-hazards model (Exact method will be used for tie data). Treatment by covariate interactions will be assessed by including the pairwise interaction terms in the Cox proportional-hazards model.

The following summary tables, figures and analysis will be provided for the ITT and PPS:

- A summary table of Kaplan-Meier estimate of TFR (protocol-defined relapse) will be presented by treatment group.
- A figure of Kaplan-Meier estimate of TFR (protocol-defined relapse) will be presented by treatment group.
- Analysis of TFR (protocol-defined relapse) will be performed using the stratified log-rank test.

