5.11.5 Infections, Serious Infection, Opportunistic Infection

- Serious adverse event in “SOC: Infections and infestations” will be summarized. Opportunistic infections are defined by MedDRA basket in Appendix.. Serious infection will be provided per 100 subject-year by treatment group during the double blind period. The patient-years will be based on the double blind period for safety analysis (see section 5.2). The rate per 100 subject-years by treatment group (along with the 95% CI) will be calculated for serious infections.

The number of serious infections per 100 subject-years is calculated as:

Total number of serious infections / Total number of subject-years \times 100

The 95% CI for the number of serious infections per 100 subject-years is calculated as follows:

Exact lower 95% confidence limit = $\text{chisq}(p = 0.025, df = 2Y) / (2T)$

Exact upper 95% confidence limit = $\text{chisq}[p = 0.975, df = 2(Y + 1)] / (2T)$

where Y is the total number of serious infections, T is total number of subject-years at risk and $\text{chisq}(p, df)$ is the quantile of the upper tail probability of the X² distribution on df degrees of freedom. This approach has the advantage of providing an estimate for the upper 95% confidence limit even when the total number of serious infections is zero.

The following summary tables will be provided.

- A summary of serious infection by SOC and PT.
- Rates of serious infections by 100 patient-years.
- A by-subject listing of Infections.
- A by-subject listing of Opportunistic Infections.

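### The double-blind safety window runs past relapse and rescue, so adverse events of rescue treatment fall under the study arm, mostly placebo, with no before/after-rescue split

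*SAP*

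**What the plan says.** SAP 5.2 defines the efficacy period first: "The double-blind period ends on the earliest day of 1) clinical cutoff date (CCOD), 2) the day before the first" treatment in the extension period, followed by end of study and last contact for patients lost to follow-up. For safety it adds: "The double-blind period ends on the same day as efficacy analysis". Neither list contains relapse, rescue therapy or a change of baseline treatment.

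The protocol places the end elsewhere. Section 4.3.2.1 ends a patient's double-blind period at a relapse, or when the 26th adjudicated event is reached. Section 4.4.1 lists "Rescue therapy for clinical relapse (leads to end of the double-blind period); pulse IV corticosteroids, intravenous immunoglobulin (IVIG), and/or apheresis".

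After a clinical relapse, Protocol 4.5.3.2 says "study drug should not be administered until the patient enters extension period". Rescued patients start open-label dosing between Day 31 and Day 60, counting relapse onset as Day 1 (Protocol 4.3.2.2, SAP 4.1). The list headed "Permitted Medication/Therapy During the Extension Period (Including After Relapse in the Double-Blind Period" permits oral corticosteroids up to 1 mg/kg/day after a relapse, against 15 mg/day as double-blind baseline treatment.

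All adverse events are collected regardless of relationship (Protocol 5.3.1). They are tabulated over the double-blind period by treatment received (SAP 5.5, 5.11). For serious infections, SAP 5.11.5 states: "The patient-years will be based on the double blind period for safety analysis". The primary endpoint, by contrast, is censored at the earliest of three dates, including "3) receiving rescue therapy for clinical relapse" (SAP 5.10.2). SAP 5.11 has no counterpart for safety.

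**The concern.** Between relapse onset and the first extension dose a patient is in a different treatment situation: blinded dosing has stopped, pulse IV steroids, IVIG or apheresis may be given, and oral steroids may be raised. Protocol 5.1.1.1 says that corticosteroids, azathioprine and mycophenolate, as used in this disease, "have been shown to be associated with infections, particularly serious infections". Section 5.1.1.12 adds immunosuppression, hypertension and diabetes for corticosteroids.

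If satralizumab prevents relapse, more placebo patients pass through this interval. Their rescue-related events then sit in the placebo column, and part of an efficacy effect appears as a safety advantage. Patient-year rates do not remove this, because the added time may carry a different risk. With infection a leading safety question, a reader should be able to see whether a lower rate on satralizumab reflects only less rescue treatment.

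**Working it through.** **Design figures reproduced.** Inputs from Protocol 6.2 and SAP 5.14: HR 0.335, two-sided 5%, 80% power, placebo hazard 0.4184 per year, 35 per arm, 10% two-year dropout, one-year accrual, 26 events.

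- Schoenfeld events: 4 × (1.960 + 0.842)² / (ln 0.335)² = 31.40 / 1.196 = 26.25. Power at 26 events is 79.6%. The plan's 26 is reproduced.
- Placebo hazard: −ln(0.658) = 0.4186, against 0.4184 stated.

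**Relapses by arm.** Exponential relapse with dropout hazard −ln(0.9)/2 = 0.0527 per year, uniform accrual and analysis at the 26th event (20,000 simulated trials) give 18.3 placebo and 7.7 satralizumab relapses. The placebo share is 18.3/26 = 70%. Time at risk before relapse is 43.7 and 55.3 patient-years. At a fixed 2.5-year analysis, the placebo share under other hazard ratios is 75% at 0.25, 68% at 0.38, 62% at 0.5, 55% at 0.75 and 50% at 1.0.

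**Post-rescue time.** Assume that every relapse is rescued and followed by extension dosing. The gap is 30 to 59 days from onset, rounded to 30-60.

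- Without truncation, placebo: 18.3 × 30/365.25 = 1.5 to 18.3 × 60/365.25 = 3.0 patient-years.
- Without truncation, satralizumab: 7.7 × 30/365.25 = 0.6 to 7.7 × 60/365.25 = 1.3.
- The clinical cutoff is the onset date of the 26th event (SAP 7.4), so relapses near it have a short gap or none. Rescue also starts some days after onset; a lag of 0-7 days is assumed.
- With both effects in the simulation, a 30-day gap with an average lag of 3.5 days gives 1.3 and 0.5 patient-years. A 60-day gap with no lag gives 2.8 and 1.2.
- Share of placebo time: 1.3/(43.7 + 1.3) = 2.9% to 2.8/(43.7 + 2.8) = 6.0%.
- Share of satralizumab time: 0.5/(55.3 + 0.5) = 0.9% to 1.2/(55.3 + 1.2) = 2.1%.

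**Serious-infection rate ratio when the drug has no effect.** Assume the gap rate is m times the usual rate. Each arm's rate is inflated by (T + m × G)/(T + G), where T is time before relapse and G is gap time.

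- m = 2, smaller G: placebo 46.3/45.0 = 1.029; satralizumab 56.3/55.8 = 1.009; ratio 0.98.
- m = 5, larger G: placebo 57.7/46.5 = 1.241; satralizumab 61.3/56.5 = 1.085; ratio 0.87.

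**Adverse-event percentages.** Assume a proportion p of rescued patients has a rescue-related event. The arm percentage rises by relapses × p / 35.

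- p = 0.10: 5.2 points placebo, 2.2 satralizumab, difference 3.0.
- p = 0.40: 20.9 and 8.8, difference about 12.

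The documents support neither value of p. The difference is an upper bound, because the tables count patients and some will already have had a qualifying event.

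**Patients who do not enter the extension.** General adverse-event reporting stops at the Withdrawal Visit, targeted at 12 weeks after the last dose (Protocol 4.5.2.3, 5.3.1). The safety follow-up calls to 24 weeks record disease medications and neurological symptoms, and the schedule marks no adverse-event collection for them (Protocol 4.5.2.4, Appendix 1 Table 6). SAP 5.2 may still count these patients' time to end of study or the cutoff, so the denominator can outrun event collection.

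**The case against.** The strongest defence is that the current window is a legitimate choice. Counting all events until the next treatment is a treatment-policy comparison, and needing less rescue is a real consequence of treatment. A cut at rescue conditions on a post-randomisation event that treatment affects. This stands, and it is why the full-window tables should stay.

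A reader might infer that the gap is time off drug. The documents do not support that. Blinded dosing is withheld, but the antibody was designed for a long half-life (Protocol 1.2), and SAP 5.2 keeps pharmacokinetic samples up to six weeks after the last dose. Infections under satralizumab plus high-dose steroids belong in the safety comparison.

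A reader might also infer that the protocol ends the period on the first day of rescue. It does not quite say so: 4.3.2.1 names relapse, and 4.4.1 says rescue leads to the end while listing it among therapies permitted during the period. The mismatch with SAP 5.2 remains.

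Other mitigations are fair. Relapse symptoms and hospitalisation for relapse are not adverse or serious adverse events (Protocol 5.2.1, 5.2.2). A separate adverse-drug-reaction table is planned, and listings would allow manual review. The infection statement in Protocol 5.1.1.1 covers background therapy that both arms receive, and the sections cited here describe no adverse effects of IVIG or apheresis. None of this gives a tabulated split at rescue.

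**Conclusion.** The point holds in limited form. SAP 5.2 and Protocol 4.3.2.1/4.4.1 give different ends for the double-blind period, and the safety tables mix time before and after rescue without separating them. The likely direction favours satralizumab. The 70% placebo share of rescue-related events rests on HR 0.335, all relapses being rescued, and the same event risk per rescue in each arm. Rescued relapses that are not protocol-defined would add to the counts.

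The size is modest: roughly 3-6% of placebo time and 1-2% of satralizumab time. The null serious-infection rate ratio of 0.98-0.87 depends on the assumed 2-5 times gap rate.

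Two stronger readings are not supported. A spurious 3-12 point gap in adverse-event percentages cannot be claimed as an estimate, since it is an upper bound on undocumented inputs. Nor can it be said that rescued patients who skip the extension supply adverse events until end of study: their general reporting stops at the Withdrawal Visit, even if their patient-years may not.

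**What to change.** - Reconcile SAP 5.2 with Protocol 4.3.2.1 and 4.4.1 on when a patient's double-blind period ends, and align patient-years with adverse-event collection for patients who do not enter the extension.
- Keep the current full-window adverse-event, serious-adverse-event and serious-infection tables.
- Pre-specify beside them the same between-arm tables with events and patient-years cut at the first day of rescue therapy. Show post-rescue events and patient-years separately by arm.
- Protocol 1.3 reports that the double-blind period is complete. If these tables have already been produced, add the split as a labelled supplementary analysis.

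The cost is one derived flag and some extra tables. Rescue start dates are recorded in the eCRF (Protocol 4.4), and SAP 7.4 already uses the first day of rescue. Sample size and alpha do not change. The cut tables need a note that satralizumab exposure persists after rescue and that rescue is itself an outcome affected by treatment.

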#### **5.3.5.3 Persistent or Recurrent Adverse Events**

A persistent AE is one that extends continuously, without resolution, between patient evaluation time points. Such events should only be recorded once on the Adverse Event page of the eCRF. The initial severity of the event should be recorded, and the severity should be updated to reflect the most extreme severity any time the event worsens. If the event becomes serious, the Adverse Event page of the eCRF should be updated to reflect this.

A recurrent AE is one that resolves between patient evaluation time points and subsequently recurs. Each recurrence of an AE should be recorded separately on the Adverse Event page of the eCRF.

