1 AMENDMENTS FROM PREVIOUS VERSION

The following changes were made in this SAP from the previous version of SAP due to the amendment to the protocol.

- Adolescents population was added based on the protocol amendment (Protocol version 8.0)
- Only treatment-emergent adverse events are collected in this study. Previously the SAP contained summaries of adverse events and treatment-emergent adverse events, the latter were removed to avoid redundancy.
- Detailed description on the identification of the following adverse event were added: serious infections, opportunistic infections, anaphylaxis, injection related reactions and injection site reactions.
- Detailed description of the following efficacy evaluation were added: EQ-5D Scoring and Visual acuity function.
- Detailed description of the immunogenicity and immunogenicity analyses were added.
- The analysis of relapse-free subjects using logistic regression will not be conducted because of a lot of early events.
- Clarify the definition of baseline ARR.
- Resolve inconsistencies mainly for scope of analysis in SAP.

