5.5 Analysis Populations

The intent-to-treat (ITT) population will serve as the primary population for the analysis of efficacy, which consists of all randomized subjects. Subjects will be analyzed as randomized for analysis purposes. In case even a subject is incorrectly stratified at time of randomization, the analysis will be performed using the stratification for randomization.

The Per-Protocol Set population (PPS) will include all subjects in the ITT population who received at least 3 doses of study drug, and without any major protocol deviations which are considered to have an impact on efficacy. Subjects will be analyzed as treated for analysis purposes in the PPS.

The Safety Set (SAF) population will include all randomized subjects who have received at least one dose of active study drug or placebo. Subject will be included in the treatment group corresponding to the trial treatment they actually received for the analysis of safety data using the SAF population, i.e. patients who received at least one dose of SA237 will be assigned to the SA237 treatment arm, irrespective of randomized arm. .

The All-Subjects-Treated (All SA237) population will be defined as all enrolled subjects who took at least one dose of active study drug at any time. Date of the first active study drug administration will be defined as Day 1 for All SA237 analysis (i.e. Day 1 of subjects allocated in placebo group is redefined on the day of first dose of SA237 when entering extension period.

The Pharmacokinetics Per-Protocol Set (PK-PPS) and immunogenicity (anti-SA237 antibody; ADA) will include all subjects in the SAF with at least 1 valid post-dose concentration result with a dosing record and sampling time. Pharmacodynamics variables will be analyzed using the SAF population.

The Adolescents population will be defined as all enrolled subjects from 12 to 17 years old (< 18 years) at the first informed consent. After the total number of protocol-defined relapses judged by the CEC reaches 26, the recruitment period for the adolescents may be continued in the extension period until a minimum of 8 adolescents are enrolled into the study.

The following summary and listing will be provided:

- A summary of analysis populations, including the number and percentage of subjects in the defined analysis sets by treatment group and overall.

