5.11 Safety Evaluation

Unless otherwise specified, all safety analyses will be based upon the SAF for double blind period and All SA237 for overall period as defined in Section 5.5.

Subgroup population was defined in Section 5.5.

If we have low numbers of AEs only listings may be provided.

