5.11.2 Adverse Events

Adverse events will be coded using most recent version of MedDRA. All summaries will be sorted alphabetically by System Organ Class (SOC) and preferred term (PT), starting with the most frequent event. All adverse events reported in whole study will be reported in listings. For AEs, if the AE intensity is missing, the worst case (severe) will be assumed. If the drug relationship is missing, the worst case (drug related) will be assumed. In summaries, multiple occurrences of the same PT event in one individual counted only once.

The following summary tables of AEs will be provided:

- An overall summary of AEs will be presented. It will include the number and percentage of subjects with at least 1 AE, serious AE, AE leading to early discontinuation of treatment, and severe AE and number of death.
- A summary of AEs by SOC and PT.
- A summary of AEs by Intensity, SOC and PT.
- A summary of AEs leading to discontinuations of treatment.
- A summary of AEs leading to drug interruption.
- A summary of adverse drug reactions (ADRs) by SOC and PT.
- A by-subject listing of all AEs.
- A by-subject listing of all AEs leading to treatment discontinuation.
- A by-subject listing of all AEs leading to drug interruption.
- A by-subject listing of all ADRs.

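### The SAP does not say how an adverse event that starts on placebo and worsens after the switch to satralizumab is allocated or graded, and the protocol asks for no date of worsening

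*SAP*

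**What the plan says.** **Recording.** Protocol 5.3.5.3 says of persistent adverse events: "Such events should only be recorded once on the Adverse Event page of the eCRF". The initial severity is entered first, and then "the severity should be updated to reflect the most extreme severity any time the event worsens". Seriousness is updated in the same way. No date of change is requested.

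**Windows.** For the double-blind safety window SAP 5.2 states: "The double-blind period ends on the same day as efficacy analysis". That is at the latest the day before the first extension dose. For All SA237, "SA237 exposure duration starts on the day of first dose of SA237". SAP 5.5 adds that "Day 1 of subjects allocated in placebo group is redefined on the day of first dose of SA237".

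**Tables.** Under SAP 5.11, "all safety analyses will be based upon the SAF for double blind period and All SA237 for overall period". The overall AE summary in SAP 5.11.2 is specified as follows: "It will include the number and percentage of subjects with at least 1 AE, serious AE, AE leading to early discontinuation of treatment", plus severe AEs and deaths.

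**Treatment emergence.** SAP section 1 removed the treatment-emergent summaries because "Only treatment-emergent adverse events are collected in this study". Protocol 6.6 still promises treatment-emergent AEs by severity.

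**Arm assignment.** The SAF definition in SAP 5.5 places anyone with one or more SA237 doses in the SA237 arm, whatever the randomized arm. It does not restrict this to doses given in the double-blind period.

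**The concern.** The reason for dropping the treatment-emergent rule holds relative to the first dose of any study drug, because Protocol 5.3.1 collects AEs from that point. It fails for All SA237. Once a placebo patient's Day 1 is moved to the first open-label dose, events already under way on placebo predate Day 1 but can still worsen on satralizumab.

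Such an event has one record, one start date and a severity and seriousness that may have arisen after the switch. The SAP gives no rule for which window it belongs to or which grade to tabulate. Because the protocol asks for no date of worsening, the analyst cannot settle this properly at the programming stage. Severe and serious AEs, and the serious infection rate, are central to the safety assessment, and counts in arms of about 35 are likely to be small.

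**Working it through.** **1. Follow one event through the rules.** A placebo patient has a moderate infection, relapses, starts open-label satralizumab, and the infection then becomes serious.

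- Record: one line, onset on placebo, seriousness now positive (Protocol 5.3.5.3).
- Double-blind table, allocated by onset date: counted under placebo as serious.
- All SA237 table, allocated by onset date: not counted, because onset precedes the first SA237 dose.
- Serious infection rate (SAP 5.11.5), allocated by onset date: in the placebo numerator, while the time in which it became serious lies outside the double-blind patient-years.
- Double-blind table with the SAF sentence read literally: the patient has had an SA237 dose and so moves to the SA237 column.

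The two readings give opposite attributions. SAP 5.3 imputes partial AE start dates, which suggests onset-date allocation, but no sentence states it. Elsewhere the SAP does handle change from a pre-existing state: treatment-boosted ADA (5.13) and marked laboratory abnormalities, which require a relevant change from baseline (7.1).

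**2. How many placebo patients could switch before the cutoff.** Inputs from SAP 5.14: 35 per arm, placebo hazard 0.4184 per year, hazard ratio 0.335, 10% dropout over two years, one year of accrual, 1.5 further years of follow-up, 26 events. From SAP 4.1: rescue-treated patients start SA237 from Day 31 to Day 60 after relapse onset.

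*Plan's own figure.* Schoenfeld events = 4 × (1.960 + 0.842)² / (ln 0.335)² = 26.25. Power at 26 events is 79.6%. The stated 26 events and 80% power are reproduced.

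*Relapses by arm at 2.5 years.* Satralizumab hazard = 0.4184 × 0.335 = 0.1402. Dropout hazard d = −ln(0.9)/2 = 0.0527. Expected relapses = 35 × the mean, over follow-up t uniform on 1.5 to 2.5 years, of λ/(λ+d) × [1 − exp(−(λ+d)t)]. This gives 18.9 on placebo and 8.1 on satralizumab, 27.0 in total.

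*Switched before the cutoff*, if every relapsing patient enters the extension:

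| Cutoff | Placebo patients switched | Their patient-years on SA237 |
|---|---|---|
| Fixed at 2.5 years, delay 30 to 59 days | 17.9 to 18.4 | 19 to 21 |
| At the 26th event (simulated, mean 2.38 years) | 16.8 | 17.4 |

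The event-driven row matches the design, so about 17 of 35. In that simulation the relapses split 18.3 placebo to 7.7 satralizumab.

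**3. Size per affected patient.** In the double-blind placebo column each patient adds 1/35 = 2.9 percentage points; 2, 3 and 4 patients add 5.7, 8.6 and 11.4. In All SA237, with about 35 + 17 = 52 patients at the cutoff, each omitted patient removes 1/52 = 1.9 points.

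**4. Number affected.** The documents give no AE rate and no rate of worsening. As an illustration only, assume 0.5 to 2 ongoing AEs per switching patient and 5% to 10% of these worsening: 17 × 0.5 × 0.05 = 0.4 to 17 × 2 × 0.10 = 3.4 AEs. This counts any worsening, including mild to moderate, so those reaching severe or serious would be fewer.

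**The case against.** A reader might infer that the plan demonstrably biases the safety comparison towards satralizumab. The documents do not support that, for five reasons.

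- Onset-date allocation is not written, and the SAF sentence read literally points the other way.
- The overwriting is not one-sided. Satralizumab-arm AEs that worsen after relapse and entry to the extension are also upgraded in the double-blind table. With 18.3 against 7.7 expected relapses, more placebo patients are exposed to this, and only theirs is worsening under the other treatment. At equal worsening rates the net effect would favour satralizumab, but that is a probable direction, not an established one.
- All SA237 has no control arm. An omission there understates satralizumab risk; it does not distort a between-arm contrast.
- One might extend the point to AEs leading to discontinuation. Protocol 5.3.5.3 covers severity and seriousness only, and SAP 5.4.1 tabulates withdrawals and their reasons separately for each period, so a stop after the switch can be seen in the right place.
- Other rules limit the loss. Protocol 5.3.5.2 gives severe or serious secondary events their own records. Protocol 5.3.5.4 and 5.3.5.5 exempt a change in severity from the ban on repeat recording of laboratory and vital-sign abnormalities, although they also speak of updating. Laboratory risks are summarised from measured values, with the All SA237 baseline reset. SAP 5.11.2 lists every AE of the whole study by subject.

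All of this stands and narrows the point. It does not remove it. Listings do not correct summary tables, two readings with opposite results need a written choice, and neither can be applied well without a date of worsening. Whether the eCRF keeps the initial severity in its own field is unknown, since eCRF version 10.0 is not among the documents.

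**Conclusion.** The gap is real and should be closed. One record per persistent AE with worst-value overwriting, safety windows split at the first SA237 dose, and no rule for events that cross the split leave both the column and the grade undefined. Under the usual but unwritten onset-date allocation, a placebo-onset AE that turns severe or serious after the switch would count against placebo and be missing from All SA237.

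On the design assumptions about 17 of 35 placebo patients could be exposed to this by the cutoff, with about 17 patient-years on satralizumab. That rests on exponential relapse and dropout, uniform entry over one year, and all relapsing patients entering the extension. Entry is optional, so the true number may be lower. Each affected patient is worth 2.9 points in the placebo column. The number affected, and so the size of any distortion, cannot be computed from the documents.

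**What to change.** In SAP 5.2, 5.5 and 5.11.2:

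1. State that AEs are allocated to a window by onset date and that, for All SA237, an increase in severity or seriousness on or after the first SA237 dose also counts as emergent.
2. Limit the double-blind tables to the severity and seriousness reached by the end of the double-blind safety period.
3. Restrict the SAF sentence on receipt of SA237 to doses given in the double-blind period.

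In Protocol 5.3.5.3 and the eCRF completion instruction:

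4. Require that a worsening after the first open-label dose be captured with its date, either as a new linked record or as a dated severity change.

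The double-blind period is complete (Protocol 1.3). For data already collected, use the audit trail kept in the EDC system (Protocol 7.1) as an approximate date of worsening and report a sensitivity table. The rule still matters for later reporting, because open-label dosing continues to 31 December 2021.

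Cost: a small protocol wording change, because single-record entry is now mandated, plus SAP text and some programming. One medical event may appear in both sets of tables, so it should be flagged as a worsening.
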